1.0 Background

Sedentary behavior (SB) is a strong modifiable risk factor for developing type 2 diabetes (T2D) and cardiovascular disease, even after controlling for daily physical activity.¹⁻³ During sedentary behavior, there is no muscle contraction of the legs, which causes decreasing insulin sensitivity, glucose uptake, vascular dysfunction, and promotes low-grade inflammatory cascades.⁴ Despite the important role of sedentary behavior in managing T2D, people with T2D remain highly sedentary. They spend on average 11-15 hours per day sitting,^{5,6} which comprises 65-75% of waking time.^{5,7,8} Moderate-to-vigorous levels of physical activity or exercise can attenuate cardiometabolic risk, but does not eliminate the increased risk associated with high sedentary time.^{1,9} Considering T2D patients' low cardiorespiratory fitness and low activity levels,^{10,11} they may be at greater risk than others for the negative cardiometabolic consequences of sedentary behavior.¹² Therefore, there is a pressing need to develop novel strategies to reduce SB and improve daily activity in patients with T2D. Targeting SB, which occupies most of a T2D patient's waking time, can be a new target behavior for secondary prevention in this population.

2.0 Rationale and Specific Aims

Frequent standing/walking can reduce the total SB time and change prolonged patterns to interrupted patterns. Since leg muscles do not contract during SB, sedentary breaks such as standing/walking (requiring muscle contractions) may change physiological pathways and improve cardiometabolic outcomes. A recent meta-analysis found that while controlling for total sedentary time and MVPA time, short sedentary breaks (2-5 minutes of standing/walking for every 20-60 minutes of sitting) were beneficially associated with cardiometabolic markers; adding one break decreases 0.05 unit of BMI, 0.2 cm of WC, 0.002 mg/dl of hsCRP, and 1.8 mmHG of systolic blood pressure (BP).^{13,14} Many intervention studies have also shown that breaking prolonged sedentary time with short periods of light PA or standing improves glucose (2-17%) and insulin (15%).^{13,15} Moreover, emerging evidence shows that **reducing SB time with frequent breaks is safe¹⁶⁻¹⁸ in other chronic health conditions and applicable to T2D patients.**

SB breaks can be achieved through self-monitoring and prompts from a wearable device. In addition, the use of a smart water bottle may be a promising strategy to naturally break sedentary time due to the impact of increased water intake on kitchen and restroom breaks. A smart water bottle can sync with an activity tracker, which could synergistically motivate the T2D patients to reduce SB. This new technique is a potentially low-cost and sustainable strategy to deliver SB reduction interventions. Because there is no SB reduction program specifically focusing on sedentary breaks in T2D patients, we propose to develop and conduct a pilot study to test a wearable technology-based SB reduction intervention in T2D patient. The 8-week intervention includes: 1) one instructional and goal setting session; 2) the use of a wearable device (Fitbit) that provides stand/walk prompts and self-monitoring; 3) a smart water bottle (HidrateSpark) that syncs with the Fitbit, and 4) weekly tailored text messages for behavior reinforcement and weekly goal monitoring. Since text messages and wearable device-based intervention requires a complex and multiple iterative process to customize research participants' needs and refine the contents and frequency of the text messages. To find the most suitable frequency and contents of text messages, we will use an iterative design process. Outcomes will be measured at baseline and post-intervention. Specifically, we aim to: **Aim 1:** Determine the feasibility and acceptability of the SB reduction intervention in T2D patients by evaluating reach, retention, satisfaction, and compliance with the

intervention.

Aim 2: Evaluate the preliminary efficacy of the SB reduction intervention on changes in total SB time and numbers of prolonged SB bouts.

Aim 3 (Exploratory Aim): Explore preliminary effects of the SB reduction intervention on light physical activity (total standing and stepping times), cardiometabolic markers (24-hour glycemic control, BMI, waist circumference, blood pressure) and patient-centered outcomes (confidence in reducing SB, habit strength for SB, and quality of life).

3. Inclusion/Exclusion Criteria

Inclusion criteria: 1) ages 18 and above, 2) diagnosed with type 2 diabetes, 3) self-reported HbA1C<13, 4) self-report of sitting \geq 8hr/day, 5) ability to stand and walk, 6) ownership of a smartphone.

Exclusion criteria: 1) currently using an activity tracker; 2) currently participating in exercise or other research programs; 3) use of insulin; 4) non-English speaking; 5) patients who are classified as unstable (e.g., heart failure, uncontrolled arrhythmia) or have kidney disease that limits daily water intake, or any other conditions contradictory to standing or walking^{19,20}; and 6) random blood glucose > 300 , and 7) currently pregnant.

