Efficacy Questionnaire for Physical Activity and Sedentary Behavior (Cronbach's alpha = 0.79).²⁵

- d) **Habit strength for SB:** Habit strength for SB will be assessed by using a validated measure, Self-Report Habit Index (Cronbach's alpha = 0.91).²⁶ This 7-item index was adapted to sedentary breaks (standing/walking) to assess the degree to which sedentary breaks become habitual.
- e) **Quality of life:** Quality of life will be measured by using the 12-item Short Form Health Survey (SF-12). The SF-12 is well-validated in T2D patients²⁷ and provides physical and mental health scores.²⁸
- f) **Medical history and current medication:** Medical history and current medication will be self-reported by the patients.
- g) **Depressive symptoms:** Depressive symptoms will be measured by using Patients Health Questionnaire 9 (PHQ-9)²⁹.
- h) **Diabetes self-management:** Self-efficacy of diabetes self-management will be measured by the Perceived Diabetes Self-Management Scale³⁰.

2. Biometric assessments

Participants will undergo a basic physical examination (e.g., height, weight, blood pressure, hip circumference, waist circumference).

- a) **Anthropometrics:** Height, weight, and waist and hip circumferences will be measured using a validated stadiometer, digital scale, and flexible tape measure, respectively. All measurements will be recorded to the nearest 0.1 cm and 0.1 kg.
- b) **Blood pressure:** Blood pressure will be measured using an automated and validated BP monitor. In a private room, participants will be seated comfortably for 5 minutes with feet flat on the ground prior to measurements.³² The device will take three readings at 2-minute intervals and the mean of three BP readings will be recorded.³²
- c) **Random glucose via finger prick:** The trained research staff will conduct a finger prick and one drop of blood will be obtained on a glucometer. The glucometer will be used to test their random glucose. Participants will NOT be required to fast overnight prior to the study visit. If the random glucose >300, the PI will be immediately informed and the participant will be withdrawn per the protocol (see section 7).

3. ActivPAL

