5.3. Intervention

The 8-week intervention will consist of four components. All study subjects will be assigned to intervention group. After the intervention, the study subjects will keep their Fitbit and the HidrateSpark smart water bottle.

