5.3.3. Smart Water Bottle

We will provide a HidrateSpark water bottle, and the study team member will assist participants in downloading the app and creating an account. The study team member

will instruct participants on how to use the bottle, with the official user manual. The device alerts participants with a color change and message on the Fitbit to keep them hydrated. The device provides the daily water intake summary in the Fitbit app. We will advise participants to drink 4.5 – 6 bottles (500ml/bottle) of water per day based on current recommendations by the U.S. National Academies of Medicine.³⁵

The HidrateSpark accounts require a unique email address for each user and the same email which is used to Fitbit account will be used to the HidrateSpark app. The same rules will be applied to the HidrateSpark account, and the account information will be stored in protected PI's computer within encrypted documents.

Once the intervention is concluded, HidrateSpark data will not be collected. Also, HidrateSpark bottle and the app will be reset for the participant to keep using the bottle.

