Participants will use the smart water bottle to increase the frequency of standing and moving by frequently going to the restroom and kitchen for refills. There is no risk associated with using the smart water bottle. To reduce the possible risk of confidentiality loss, we will create an anonymous email account for the HidraSpark app. All identifiable data will be kept on password-protected computer systems in a locked office.

8-Week Sedentary Behavior Intervention

Participants will gradually decrease their sedentary behavior and replace the sedentary behavior with a short period of light intensity physical activity such as 2 to 3 minutes of standing or walking over 8 weeks. The risk of falling or injury is the same as would be associated with day-to-day activity. Study staff members will instruct participants to make sure there are no hazards within the walking path and surrounding area.

Suicidal ideation or severe distress

Research has confirmed that simply asking a participant about whether they have thoughts of suicide is not a likely trigger of such an event⁴¹. It is usually only when the person reports ideation as well as an intent, plan, and/or means to commit suicide that risk for immediate suicide is considered to be more acute.

If a participant reports severe distress or suicidal ideation during the survey administration (Baseline visit 2 or Post-intervention visit), the research staff will immediately notify the PI. The PI will provide the participant with help to get treatment. This may include:

- working with the participant to contact his/her doctor,
- contact a trusted family member, or a therapist to discuss his/her thoughts,
- or work with the participant on a plan that may include getting him/her to a hospital for safety.

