8.0 Statistical Considerations

Sample Size Calculation

Because this is a novel intervention, we cannot use an exact effect size from the literature. As of today (May 22), we have recruited 16 participants; 3 have withdrawn, 5 randomized into intervention group, 8 assigned to control group. For the remaining iterative process, each cohort will have 10 participants. It will give us enough power to be saturated in terms of qualitative findings. Assuming a 15% attrition rate, we plan to enroll 24 more participants, for a total of 40 participants.

Analysis Strategies

Aim 1: Feasibility and acceptability outcomes will be reported as percentages or averages. For the exit interview, we will collaborate with the Vanderbilt Qualitative Research Core in developing a semi-structured interview guide and thematic analysis. To enhance credibility, we will follow the consolidated criteria for reporting qualitative research (COREQ) guidelines.⁴⁴

Aims 2 & 3: Descriptive analyses are planned to characterize the study sample on all measures including baseline demographics and covariates. For this pilot study, exploratory linear mixed modeling will be used to provide descriptive statistics relative to treatment effects, both within- and between-groups effects on the primary and secondary outcomes over time. We will also estimate effect sizes for those outcomes.

Exit Interview

We will develop a semi-structured interview guide and thematic analysis. The exit interview will be audio recorded, transcribed verbatim, and analyzed using a thematic approach to guide refinements to future SB reduction interventions as well as identify barriers and facilitators to SB reduction. To enhance credibility, we will ensure methodological triangulation (audio recording, surveys, and field notes), audit trail and peer-debriefing process.⁴⁵

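### Exclusion criterion 5 bars a limit on water intake only when kidney disease is the cause, so a person with a non-renal fluid limit is not clearly excluded from advice to drink 2.25 to 3.0 L a day

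*Combined protocol and SAP*

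**What the plan says.** Exclusion criterion 5, in Section 3 (Inclusion/Exclusion Criteria), has three parts:

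- It excludes "patients who are classified as unstable (e.g., heart failure, uncontrolled arrhythmia").
- It excludes those who "have kidney disease that limits daily water intake".
- It ends with a catch-all for other conditions that would make standing or walking inadvisable.

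Section 2.0 explains that the smart bottle is expected to break up sitting "due to the impact of increased water intake on kitchen and restroom breaks". Section 5.3 states: "All study subjects will be assigned to intervention group". Section 5.3.3 sets the target: "We will advise participants to drink 4.5 – 6 bottles (500ml/bottle) of water per day". It adds that the bottle prompts drinking by a color change and a message on the Fitbit. In Section 6.0, the paragraph on the bottle says: "There is no risk associated with using the smart water bottle".

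On numbers, Section 8.0 says: "we plan to enroll 24 more participants, for a total of 40 participants".

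**The concern.** The second part of criterion 5 does not exclude kidney disease as such. It excludes kidney disease that restricts how much water a person may drink. The plan has therefore already judged that a restriction on water conflicts with this intervention, and that reasoning does not depend on which organ is responsible. Yet a restriction with any other cause is not mentioned.

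What is at stake is participant safety. Drinking more is part of how the intervention is meant to work. Someone under a clinician's fluid limit could be advised, and then prompted by the device over 8 weeks, to drink an amount that conflicts with that limit.

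**Working it through.** **Advised volume.** Section 5.3.3 gives bottles per day and volume per bottle but prints no total.

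- Lower end: 4.5 × 500 ml = 2,250 ml = 2.25 L a day.
- Upper end: 6 × 500 ml = 3,000 ml = 3.0 L a day.

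**Who would receive the advice.** Section 8.0 gives a planned total of 40, with 16 already recruited.

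- Still to enroll: 40 − 16 = 24, which reproduces the plan's own figure.
- The first 16 were 3 withdrawn + 5 intervention + 8 control = 16.
- Under Section 5.3 all 24 new participants are due the intervention, including the water advice.

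**Criterion 5 applied to a person with a non-renal fluid limit.**

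| Part of criterion 5 | Does it exclude this person? |
|---|---|
| Classified as unstable | Only if the person is classed as unstable. Nothing links this part to fluid. |
| Kidney disease limiting water | No. The cause is not renal. |
| Catch-all | Only if standing or walking is also inadvisable. |

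No other inclusion or exclusion criterion mentions fluid or water. Heart failure depends on the reading of the first part. If its appearance as an example means that heart failure itself counts as unstable, it is already excluded. If only unstable heart failure is meant, a stable patient with a fluid limit is not.

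**Other safeguards in the text.**

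- *Eligibility confirmation (Section 4.0).* Staff confirm eligibility before the baseline visit is scheduled. The written criteria they would check against omit non-renal limits.
- *Chart access (Section 4.0, Reporting Workbench).* The record can be opened for further screening, but this is described for that recruitment route only and no fluid check is mentioned.
- *Baseline questionnaire (Section 5.1, item f).* "Medical history and current medication will be self-reported by the patients". This follows consent, and no step connects the answers to the water advice.
- *Discontinuation (Section 7.0).* The investigator may stop a participant for whom continuing would be harmful. This acts after enrollment, and the listed criteria do not name a fluid limit.

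None of these is described as a check for a fluid limit.

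**The case against.** The strongest case against is that the gap is narrow and perhaps empty.

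- In criterion 5 arrhythmia is qualified as uncontrolled while heart failure carries no qualifier, so the more natural reading may be that all heart failure is excluded. The list is also only of examples, which lets staff class other serious conditions as unstable. This has force: it may remove the one relevant non-renal condition that the protocol names. It does not supply a rule for a fluid limit in a person judged stable.
- The documents identify no affected group and give no frequency. That is true, and it limits the size of the point. The argument is about what the criterion says and does not need a count.
- The screening survey and consent pages are not available, and a question or warning could sit there. This stands as a limit: the wording of the criterion can be judged, but whether anyone would in practice go unscreened cannot.
- The target is advice, described as based on national recommendations. It is not a condition of staying in the study, and the compliance measures in Table 2 do not include water intake. A person under a fluid limit could simply follow their clinician. This lowers the risk, but the plan did not treat it as sufficient for kidney disease.

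**Conclusion.** The concern holds as a minor wording gap with a safety purpose. As written, criterion 5 does not clearly exclude a person with a non-renal fluid limit, and the water advice carries no exception for such a person. The advised amount is 2.25 to 3.0 L a day during the 8-week intervention, and the exposure concerns at most the 24 participants still to be enrolled. The number actually affected is unknown and may be zero.

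The conclusion rests on the text of the criteria and on the absence of any described check for a fluid limit. It would shrink to a matter of tidying the protocol if the screening survey already asks the question. Estimates, power and analysis are untouched.

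**What to change.** Reword the second part of criterion 5 so that it excludes a medical limit on daily water intake whatever its cause, including kidney disease. Ask this as one question at the eligibility call, for example whether a clinician has told the person to limit daily water or fluid. No volume or clinical threshold is needed.

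Two further edits are optional. Setting out the three parts of criterion 5 as separate items would make them easier to apply consistently. The statement in Section 6.0 that the bottle carries no risk could be confined to participants without such a limit.

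The cost is one reworded criterion and one screening question, plus one qualified sentence if the Section 6.0 edit is made. A few otherwise eligible people may be lost, but they are people for whom the water component would be unsuitable. If the survey already asks, the change only brings the protocol into line with practice.

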4.0 Enrollment

Recruitment

We will use five recruitment strategies:

1) Self-referrals

Recruitment flyers and brochures will be posted in Primary care clinics at Vanderbilt for self-referrals. The flyer and brochure are attached to this application. If the subject is interested, they will call the number on the recruitment flyers. During the phone call, the trained research staff will answer any questions from the potential participants and ask about their eligibility. Any of the data regarding their eligibility will not be recorded or stored. If subjects are interested in participating and meet all the eligibility criteria, an in-person baseline visit will be scheduled. The detailed procedure regarding pre-screening prospective participants is described below

2) Research Notification Distribution List

Email distribution list allows researchers to email IRB-approved participant recruitment announcements to the Vanderbilt community. Members of the distribution list have the option to subscribe/unsubscribe with each email. The potential participants will click the pre-screening consent. The detailed procedure regarding pre-screening prospective participants is described below

3) ResearchMatch.

ResearchMatch is a national electronic, web-based recruitment tool that was created through the Clinical and Translational Science Awards Consortium in 2009 and is maintained at Vanderbilt University as an IRB-approved data repository (see IRB #090207). The detailed procedure regarding pre-screening prospective participants is described below.

After advertisement, there will be two approaches to identify eligible participants. For online recruitment (using Email distribution list and ResearchMatch) placed via email, there will be a link directing the potential participants to the prescreening e-consent via REDCap. They will have an

option to download the e-consent for prescreening activities. After they sign on the prescreening e-consent, they will answer several questions about their eligibility (e.g. sitting hours > 8 hours a day). These pre-screening data will be saved into REDCap. Once they meet all the inclusion criteria, the trained research staff will call them to confirm their eligibility and schedule an in-person baseline visit.

4) Reporting Workbench

Reporting Workbench Reports are available/viewable in eStar. These reports are developed using real-time data and can be customized to meet study-specific inclusion/exclusion criteria that are computable in the EHR. The reports often include additional variables to facilitate study team outreach, such as Research OK to Contact status, MHAV account status, contact information, next upcoming appointment in a specific clinic. While the report displays certain variables/data, it provides easy access to a patient's record for additional screening and confirmation of eligibility. Research team members with appropriate eStar access can view/run the reports as frequently as needed.

We plan to use the results from our custom Reporting Workbench report to facilitate outreach in the following way: To send My Health at Vanderbilt (MHAV) recruitment requests, as detailed below in recruiting strategy 5. KSP do not have an existing provider relationship with the patients being approached about study participation. Results will be restricted to those marked as 'OK to Contact'. We will not be reaching out to employees or persons of interest.

5) My Health at Vanderbilt (MHAV) Recruitment Requests

Participants will be recruited through My Health at Vanderbilt. My Health at Vanderbilt (MHAV) is VUMC's patient portal where the patient may sign up and participate in managing his/her health care. MHAV can also be used for sending recruitment requests to a predefined cohort of patients who meet certain study-specific inclusion/exclusion criteria, have an activated MHAV account and are marked as OK to Contact in eStar. The recruitment requests are sent by a central VICTR team on behalf of the study team. The notification preferences for the recruitment requests can be managed by the patients in MHAV. The system default is an email notification like clinical notifications (see attached MHAV Recruitment Request messaging). If the patient has turned off notifications, the study will just be listed on their research studies page in MHAV.

Once the Recruitment Requests are sent, the patients' enrollment status is automatically updated to (IT Use Only) Identified - RWB Recruitment Message or Auto DL. If the patient clicks '**No Thank You**', the patient's enrollment status in eStar is automatically updated to (IT Use Only) **Not Interested - Pt. answered in MHAV**. The study team does not get a notification in Epic In Basket or in REDCap.

If the patient clicks '**I'm Interested**', the designated KSP (with eStar access) receive an In Basket message in eStar indicating the patient is interested

The patient's enrollment status is automatically updated to (IT Use Only) **Interested - Pt. answered in MHAV**. The REDCap Participant Updater Module looks for the patient's MRN in the study specific database. If a matching MRN is not found, the Participant Updater Module creates a record in the study-specific database with the following information from eStar:

- (1) Patient's MRN

- (2) Patient's enrollment status - (IT Use Only) Interested - Pt. answered in MHAV
- (3) Study ID (IRB#)

REDCap CDIS is then triggered to pull in the patient email address from eStar if available for all patients who click I'm Interested. This will trigger an email from REDCap to the patient which contains a link to the IRB approved pre-screening and eConsent surveys on REDCap.

[figure not shown]
If the patient responds to the email from REDCap or completes a pre-screening survey or eConsent, the study team will update the patient's enrollment status accordingly in eStar or REDCap. Once the patient's enrollment status has been updated in the study specific record in REDCap, the Participant Updater Module will automatically update the enrollment status in eStar. The study team will contact the interested patient by telephone call or email to confirm their eligibility and schedule an in-person baseline visit

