5.1. Baseline visit 1: Initial contact, screening, and consent

Interested respondents will be screened by a trained research staff over the phone or in-

person, depending on the recruitment methods. For this research, no aspect of the participant's diabetes treatment regimen will be modified.

Those who are eligible for the study will be invited to the in-person visit. The first visit (i.e. Baseline visit 1) will be conducted at VUSN (Vanderbilt School of Nursing)'s lab at Wesley building.

At the Baseline visit 1, the trained research staff will ask the individual what their most recent blood glucose level was. If their reported glucose levels are between 80-300, they will complete the informed consent with assistance from the trained research staff.

Those who are consented will participate in 1) completing survey questionnaires (30minutes), 2) biometric assessments 3) brief instruction regarding the wear of activPAL and continuous glucose monitoring (CGM) devices (30 minutes), and 4) start to wear two devices for 7 days. The activPAL3 device (PAL Technologies Ltd., Scotland, UK) will be worn on the thigh and a CGM (Abbott FreeStyle Libre) will be attached to the upper arm. The research staff will provide 1) a copy of the informed consent form; 2) instructions with photos and 5 waterproof dressings (Tegaderm) for attaching the activPAL on the thigh; 3) information about the CGM; and 4) daily sleep diary and wear log for 7 days. Participants will receive \$25 for baseline visit 1.

1. Questionnaires

Participants will be given an iPad to answer questions about their demographics, socioeconomic characteristics, and a series of questionnaires detailed below. All responses will be recorded in REDCap.

- a) **Demographics:** demographics and socio-economic status will be self-reported by the patients.
- b) **Health behavior:** Questions about their tobacco use, alcohol intake, physical

activity (measured using the 16-item Global physical activity questionnaire²¹), sedentary behavior (measured using 11-item Weekly sitting inventory²²), and diet (measured using the 16-item Rapid Eating and Activity Assessment for Participants Short Version (REAP-S)²³, sleep quality (measured using the 10-item Pittsburgh sleep quality index²⁴) will be answered with the assistance of the study team member.

c) **Confidence in reducing SB and increasing PA:** Confidence in reducing SB and increasing physical activity will be measured using 12 items from the Self-

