Participants will answer the same questions about their demographics, socioeconomic characteristics, medical history and current medication, health behaviors, and patient-centered outcomes (e.g., fear of movement, confidence in reducing SB and increasing PA, habit strength for SB, quality of life, and depressive symptoms). Participants will have a choice to complete these questionnaires during the post-intervention visit in person or to receive paper copies of the questionnaires by mail. Printed copies will be identified by the participant's REDCap record ID number; there will be no additional identifying information on the printed questionnaires. If a participant chooses to receive the questionnaires by mail, he or she will be asked to complete them using a blue or black ink pen no sooner than 2 days prior to their scheduled post-intervention visit and will bring the completed surveys to their post-intervention visit. After the post-intervention visit is completed, the study team will enter their responses manually into REDCap and upload a scanned PDF version of the paper questionnaires to their REDCap record. Paper copies of the surveys will be kept in a locked cabinet in the study team's office at the Vanderbilt School of Nursing. In addition, participants will answer questions (Table 2) about feasibility and acceptability of the intervention. Level of satisfaction with the intervention will be assessed by using 23 items from the questionnaire developed by Lyons, Swartz, Lewis, Martinez and Jennings ³⁹ and Burner, Zhang, Terp, Bench, Lee, Lam, Torres, Menchine and Arora ⁴⁰. We will also use the 10-item of System Usability Scale⁵⁵ to assess usability. The scale is considered as "industry standard"

and provides a global measure of satisfaction ⁵⁶.

Table 2. Feasibility and Acceptability Assessment

Variables	Measures
Reach	(participants enrolled/participants screened and eligible) × 100
Retention	(participants completing post-intervention assessment/participants enrolled) × 100
Satisfaction	23 items from Lyons and Burner's questionnaires, System usability scale, Exit interviews (n=20)
Compliance	Number of days the Fitbit device was worn by week Number of days the Fitbit app was logged in by week

Number of text messages replied about the next week's goal

2. Biometric assessment

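### Reach (Aim 1) needs a count of everyone screened and eligible, but eligibility data from self-referral phone calls are not to be kept and no tally is described, so eligible callers who decline before booking drop out of the denominator

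*Combined protocol and SAP*

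**What the plan says.** Aim 1 (section 2.0) judges feasibility and acceptability "by evaluating reach, retention, satisfaction, and compliance with the" intervention. Table 2 in section 5.4 gives the formula for reach as ("participants enrolled/participants screened and eligible") × 100. It covers all recruitment routes. Under Analysis Strategies, section 8.0 adds only this: "Feasibility and acceptability outcomes will be reported as percentages or averages".

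Section 4.0 lists five recruitment strategies. Under self-referral, a person who has seen a flyer or brochure phones the study, and staff answer questions and ask about eligibility. The plan then states: "Any of the data regarding their eligibility will not be recorded or stored". The next step is conditional: "If subjects are interested in participating and meet all the eligibility criteria, an in-person baseline visit will be scheduled".

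The online routes (email distribution list and ResearchMatch) are handled differently. Respondents sign a pre-screening e-consent and their answers are saved in REDCap. For the patient portal route, the record created when a patient signals interest holds the medical record number, enrollment status and study ID, but no eligibility result. The patient is then emailed a link to the pre-screening survey, and staff later "contact the interested patient by telephone call or email to confirm their eligibility".

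Section 5.1 returns to screening ("Interested respondents will be screened by a trained research staff over the phone" or in person), and Table 3 lists screening by phone or in person as a stage of its own. Neither mentions a screening log or a count.

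**The concern.** The denominator of reach is a count of people found eligible at screening, whether or not they went on to enroll. On the self-referral route, screening takes place during the phone call, and the plan says that what is learned there is not kept. The first trace the plan describes for a self-referred person is a booked visit, which requires both eligibility and interest. Someone who phones, is found eligible and then decides against taking part belongs in the denominator but appears in no described record. Self-referred people who do enroll remain in the numerator.

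The group that goes missing is exactly the group reach is meant to capture: eligible people who were offered the study and said no. A count not made at the time of the call may not be recoverable later. What is at stake is the accuracy of one named Aim 1 percentage. No reach target or progression threshold is stated, and neither the sample size nor Aims 2 and 3 depend on it.

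**Working it through.** **Inputs from the plan**

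- Reach = enrolled / (screened and eligible) × 100 (Table 2, section 5.4).
- Planned enrollment: "we plan to enroll 24 more participants, for a total of 40 participants" (section 8.0), with 16 already recruited at the May 22 status.
- The plan states no value or target for reach, and no number of people screened, eligible or declining.

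**The plan's own figure.** The planned numerator can be reproduced. Two remaining cohorts of 10 give 20 (the number of cohorts is an assumption; only the cohort size is stated). Allowing for 15% attrition, 20 / (1 − 0.15) = 23.5, rounded up to 24, and 16 + 24 = 40. Reach itself cannot be reproduced, because the documents give no denominator.

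**Who can be counted on the self-referral route**

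| Caller | Belongs in the reach denominator? | Trace described in the plan |
|---|---|---|
| Eligible and books a visit | Yes | The scheduled visit |
| Eligible, declines before booking | Yes | None |
| Not eligible | No | None needed for reach |

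Only the second row is a problem. Eligible callers who book can be counted even if they do not later enroll.

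**Direction and size.** Let E be the number enrolled, R the eligible people recorded on all routes, and L the eligible callers who decline before booking and go unrecorded.

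- Reported reach = E / R
- True reach = E / (R + L)

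Since L cannot be negative, reported reach is never below true reach through this mechanism, and the two are equal when L = 0.

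With E = 40, and with R and L assumed because the documents give neither:

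| R | L | Reported reach | True reach | Overstatement (points) |
|---|---|---|---|---|
| 80 | 0 | 40/80 = 50.0% | 40/80 = 50.0% | 0 |
| 80 | 5 | 50.0% | 40/85 = 47.1% | 2.9 |
| 80 | 10 | 50.0% | 40/90 = 44.4% | 5.6 |
| 80 | 20 | 50.0% | 40/100 = 40.0% | 10.0 |
| 50 | 0 | 40/50 = 80.0% | 40/50 = 80.0% | 0 |
| 50 | 5 | 80.0% | 40/55 = 72.7% | 7.3 |
| 50 | 10 | 80.0% | 40/60 = 66.7% | 13.3 |
| 50 | 20 | 80.0% | 40/70 = 57.1% | 22.9 |

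For a given L, the error is larger when R is smaller. The calculation does not assume any particular share of self-referrals, or that reach is equal across routes.

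**The case against.** The strongest reply is that the sentence is a privacy rule about individual answers. Online respondents sign a pre-screening e-consent before their answers are stored; phone callers have signed nothing, so not keeping their answers is coherent and does not forbid an anonymous count. That is a fair reading, and an identifier-free tally is compatible with it. But the plan describes no such tally, and staff who follow the sentence literally could keep nothing.

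A second reply is that the group is small: a caller must be interested enough to phone, be found eligible, and then decline before booking, on one of five recruitment strategies. This may well be so. Nothing in the documents shows the number to be large, and the highest illustrative figure needs decliners on this one route to be 20 of 70, or 29%, of all eligible people. Still, the plan makes booking conditional on interest after the caller's questions have been answered, so it allows for callers who are not interested.

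A third reply is that the denominator could mean people whose eligibility was verified later. Section 9.0 places consent after verification of eligibility, and section 5.1 asks about recent glucose at the first visit before consent. Under that reading a phone decliner would not count. However, Table 3 treats phone screening as its own stage, and Table 2 does not limit the denominator to people who attended a visit. That reading would also need to be written down.

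It is also true that the other routes are not fully specified. The net error in overall reach is therefore not established, but gaps elsewhere do not repair this one.

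**Conclusion.** The concern holds. The records described in the plan do not supply the Table 2 denominator whenever an eligible self-referred caller declines before booking, and the effect of this mechanism is to overstate reach. Its size is unknown and may be zero. The illustrations run from 0 to 10.0 points with 80 eligible people recorded, and from 0 to 22.9 points with 50, and they rest on assumed counts apart from the 40 enrolled. The absence of any described count is clear from the text; a material bias in reach is not shown. Because no decision rule uses reach, this is a point the plan should correct, but not one that threatens the study's other results.

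**What to change.** Amend the self-referral paragraph in section 4.0 to say that no identifiable eligibility data from these calls are stored, but that an identifier-free count is kept of callers screened, callers eligible, and eligible callers who declined. State beside Table 2 that this count enters the reach denominator, and note the recruitment route of each enrollee.

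For calls taken before the change, if no count exists, report overall reach both with the self-referral route and without it (removed from numerator and denominator alike), and state the limitation. The version without it describes reach on the other routes only and should be labeled so. Reporting reach route by route is optional.

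The cost is a small IRB wording amendment and a tally sheet. At the May 22 status, 16 of the planned 40 (16/40 = 40%) were already recruited, so a tally started then could cover recruitment of the remaining 24 (24/40 = 60%). The documents do not say whether any count of earlier calls exists; the study team should check before resorting to the fallback.
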